7.2 Sample Size

Based on previous retrospective epidemiological studies (Kupila et al and Michael et al) we expect to see the following number of cases.

58	No meningitis	Bacterial Meningitis	Aseptic meningitis	HSV-2 meningitis	VZV	Enterovirus
1066	682	160	223	38	18	58

This is based on Michael et al's study(36) finding 217 patients with suspected CNS infection over a 3 month period in 10 hospitals in the North West of England. 18 of these patients had aseptic meningitis, 13 had purulent meningitis and 55 just had meningism. I have, therefore, extrapolated that there were 86 patients with suspected meningitis (although this may be an underestimate.) Only 5 of the patients with aseptic meningitis had viral PCRs done and 1 of these (20%) was positive for HSV-2. Although this is clearly a small number it is similar to Kupila et al(5) who found 17% of their aseptic meningitis cases had HSV-2. They also found 26% with enterovirus and 8% with VZV.

I have extrapolated the numbers from Michael et al's study to calculate the expected numbers over a year and in 31 centres. I have calculated the expected prevalence of different viruses from the data in Kupila's study.

It is likely that this is an underestimate as it is based on retrospective data.

Using the HES data(3) there were 2741 finished consultant episodes of viral meningitis in England in 2009-2010. Based on the fact that the North West region has 13% of England's population (Census data) we could expect up to 356 cases of viral/aseptic meningitis in one year.

For this type of study approximately 50 patients are needed as a minimum. For comparisons between diagnostics groups (eg herpes meningitis versus bacterial meningitis), a minimum of 25 patients would be needed in each group to have 90% power to show a

difference of one standard deviation in the measure of interest, allowing for approximately 10% drop out. We are likely to have at least this number of patients with herpes meningitis, and probably many more.

7.3 Analysis Plan

Normally distributed data will be compared using Student's T test, and non-parametric tests, such as the Mann-Whitney U test, used for other data. Multiple logistic regression e.g. Cox regression, will be used to look for features predictive of particular pathogens. This will be adjusted for age and gender. Differences in median time to symptom resolution between groups will be analysed using two-sided actuarial (log-rank) methods, with a conventional 5% (type I error) significance level. The outcome analysis will also be adjusted for different research sites using multi-level modelling.

Assistance with analysis will be given by [name], Senior Lecturer in Epidemiology.

8 Safety Considerations

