1 PROTOCOL SUMMARY

Title: UK Meningitis Study: Epidemiology and outcomes in meningitis in the UK – A prospective, observational, cohort study.

Population: A study looking at adults admitted to hospitals in the UK with suspected meningitis.

Inclusion Criteria

- a. 16 years or over
- b. Suspected Meningitis AND either
 - i) Have had or are going to have a lumbar puncture
OR
 - ii) If Lumbar puncture is contraindicated: the clinician has a strong suspicion of meningitis AND positive blood culture for bacterial pathogen consistent with meningitis OR radiology consistent with meningitis AND being treated as meningitis.

Exclusion Criteria

1. Patients with indwelling ventricular devices (EVD, VP shunts etc...) or iatrogenic meningitis
2. Patients in whom a lumbar puncture is contraindicated (except see b(ii) above)

Number of Sites: 35-45

Study Duration: 2 years extended to 5 years

Objectives:

[figure not shown]
Primary:

- To determine the prevalence of viral meningitis in adults hospitalised with suspected meningitis and how much of viral meningitis is attributable to herpes viruses, and other viruses.

Secondary:

- To examine the clinical and laboratory features, time to symptom resolution, neurological complications, neuropsychological sequelae, and recurrences in viral meningitis
- To compare these features and outcomes with those in bacterial meningitis and non-meningitic controls
- To prospectively evaluate the *Meningitest* – an algorithm for predicting viral or bacterial aetiology in meningitis
- To determine the number of people with aseptic meningitis being offered an HIV test and the proportion of these that are positive.
- To determine and describe the causes of aseptic meningitis in our region.
- To determine the costs to the NHS and to the patients.
- To determine the impact on the patient's quality of life.
- To evaluate the use of certain outcome measures in viral meningitis (HIT, ABNAS).
- To use these epidemiological and disease burden data to design a phase III study of aciclovir / valaciclovir in herpes meningitis.
- To evaluate new genomic and proteomic approaches in the diagnosis of meningitis.
- To evaluate new diagnostic techniques and methods
- To identify themes and barriers amongst clinicians and laboratory staff that may be associated with implementing new diagnostic tests for meningitis.

Schematic of Study Design

1.1 Substantial Amendment 17

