POSSIBLE VIRAL MENINGITIS

Suspected meningitis AND

CSF white cell count >4 leukocytes per ml of CSF**

AND laboratory detection of organism outside the CNS (e.g. stool, throat, genitals etc...).

PURULENT MENINGITIS (suspected bacterial meningitis)

Suspected Meningitis AND

CSF WCC 20-1000 leukocytes per ml of CSF** and predominantly polymorphonuclear cells,
OR

CSF WCC >1000 (any predominant cell type)

AND

CSF/plasma glucose ratio <40%(if paired glucose taken).

PROVEN BACTERIAL MENINGITIS

Suspected meningitis

AND

CSF with >4 leukocytes per ml of CSF**

AND

Detection of appropriate bacterial pathogen from blood or CSF (culture, nucleic acid detection or serology)

Some patients who are admitted and have a lumbar puncture for suspected meningitis may turn out to have encephalitis. This would be defined as(13):

ENCEPHALITIS

Altered consciousness for >24 hours (including lethargy, irritability or a change in personality)

With 2 or more of the following

- Fever or history of fever (≥ 38 degrees Celsius) during the current illness
- Seizures and/or focal neurological signs (with evidence of brain parenchyma involvement)
- CSF pleocytosis (>4 leukocytes)
- EEG suggesting encephalitis
- Neuroimaging suggestive of encephalitis (CT or MRI)

WITH NO OTHER CAUSE FOUND.

***A bloody tap will falsely elevate the CSF white cell count and protein. To correct for a bloody tap, subtract 1 white cell for every 700 red blood cells/mm³ in the CSF, and 0.1 g/dl of protein for every 1000 red blood cells(14).*

CONTROLS

[figure not shown]
Our control group will be the group of patients who have had a lumbar puncture for suspected meningitis but are subsequently found not to have meningitis i.e. the LP shows no features of viral, bacterial or aseptic meningitis (less than or equal to 4 leukocytes/ml).

Information will be obtained on discharge diagnosis and follow up will be as for the meningitis cases. The control group will be further subdivided into:

- a) Those who have a normal CSF and no other significant illness (as determined by members of the study management team) causing their symptoms
- b) Those who have a normal CSF but have a significant systemic illness contributing to their symptoms e.g. pyelonephritis, pharyngitis, HIV seroconversion illness etc...
- c) Those who have a normal CSF leukocyte count but abnormal CSF in other ways indicating another neurological condition causing their symptoms e.g. subarachnoid haemorrhage.

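### Section 7.3 names the pooled-variance Student's t test for diagnostic groups that 7.2 expects to be very unequal in size, so its 5% level rests on an unstated assumption of equal SDs

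*Protocol*

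**What the plan says.** Section 7.3 (Analysis Plan) fixes the simple comparisons in one sentence: "Normally distributed data will be compared using Student's T test, and non-parametric tests, such as the Mann-Whitney U test, used for other data". It sets no equal-variance condition and gives no unequal-variance alternative. The only significance level in 7.3 belongs to the time-to-resolution analysis, which uses "two-sided actuarial (log-rank) methods, with a conventional 5% (type I error) significance level". Outcomes are also to be adjusted for site by multi-level modelling, and nothing is said there about variances.

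Section 7.2 (Sample Size) justifies the comparisons with equal groups and one common SD: "For comparisons between diagnostics groups (eg herpes meningitis versus bacterial meningitis), a minimum of 25 patients would be needed in each group", for 90% power at a difference of one SD with about 10% drop-out. Its table of expected cases reads "1066 682 160 223 38 18 58": in total 1066, then no meningitis 682, bacterial 160, aseptic 223, HSV-2 38, VZV 18 and enterovirus 58. No SD is given for any outcome in any group.

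The contrasts are those named in 7.2 and in the secondary objective of section 1, "To compare these features and outcomes with those in bacterial meningitis and non-meningitic controls".

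**The concern.** The calculation in 7.2 assumes equal groups, where Student's test tolerates unequal SDs well. The groups that 7.2 expects are far from equal. With 38 against 160 or 682, the pooled variance is mostly that of the large group, while the true variance of the difference in means is mostly that of the small group. If the two SDs differ, the standard error is wrong: too small when the small group is the more variable, too large when it is the less variable.

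The document gives some reason to doubt equal spread. Section 5.1 makes the controls a mixture: "The control group will be further subdivided into" three sets, namely patients with no other significant illness, with systemic illness, or with another neurological condition. The ABNAS (Appendix C) is a bounded scale of 24 items scored 0 to 3. Section 6.5.1 asks people without headaches to tick the lowest option on every HIT item, which gathers them at one end. On such scales the spread often changes with the mean.

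At stake are false or missed differences between diagnostic groups in secondary outcomes, some of which are to inform the planned phase III trial.

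**Working it through.** **Inputs.** Group sizes are from the table in 7.2, taking herpes as HSV-2 alone. The two-sided 5% level is carried over from the log-rank sentence in 7.3, which is an assumption. The SD ratio r (smaller group over larger group) is also an assumption, since the protocol gives none; 0.5 to 2 was explored.

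**The plan's own figures.** With a difference of one SD, two-sided 5% and 90% power, n = 2(1.96 + 1.2816)² = 21.01, so 22 per group; the exact t solution is 22.02. Dividing by 0.9 for drop-out gives 24.5, so 25, as stated. The expected counts also reproduce. Going from 10 hospitals over 3 months to 31 centres over a year is a factor of 4 × 3.1 = 12.4, so 86 → 1066, 55 → 682, 18 → 223 and 13 → 161 (stated as 160). Then 17%, 8% and 26% of 223 give 38, 18 and 58.

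**Type I error of Student's test.** Set the larger group's SD to 1. Then

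- pooled variance: s² = [(n₁ − 1)r² + (n₂ − 1)] / (n₁ + n₂ − 2)
- variance the test uses: V_P = s²(1/n₁ + 1/n₂)
- true variance: V_T = r²/n₁ + 1/n₂
- large-sample type I error: 2[1 − Φ(1.96 √(V_P/V_T))]

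| n₁ v n₂ | r | s² | V_P | V_T | √(V_P/V_T) | Type I error |
|---|---|---|---|---|---|---|
| 38 v 160 | 1.5 | 1.236 | 0.0403 | 0.0655 | 0.784 | 12.4% |
| 38 v 160 | 0.67 | 0.896 | 0.0292 | 0.0181 | 1.271 | 1.3% |
| 38 v 682 | 1.5 | 1.064 | 0.0296 | 0.0607 | 0.698 | 17.1% |
| 38 v 682 | 0.67 | 0.972 | 0.0270 | 0.0133 | 1.426 | 0.5% |
| 25 v 25 | any | (r² + 1)/2 | = V_T | = V_P | 1 | 5.0% |

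**Simulation** (20,000 data sets per setting, normal data, equal means):

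| n₁ v n₂ | r | Student | Welch | Mann-Whitney |
|---|---|---|---|---|
| 25 v 25 | 1.5 | 5.1% | 5.0% | 5.1% |
| 160 v 223 | 1.5 | 6.5% | 5.0% | 6.1% |
| 38 v 160 | 1.5 | 12.6% | 5.2% | 8.7% |
| 38 v 160 | 0.67 | 1.3% | 5.0% | 2.4% |
| 38 v 682 | 1.5 | 17.2% | 5.2% | 9.9% |
| 38 v 682 | 0.67 | 0.5% | 5.1% | 1.5% |

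At r = 2, Student's test reaches 17.9% (38 v 160) and 28.1% (38 v 682). With equal SDs every test is near 5% at all sizes. Welch's test stayed between 4.6% and 5.2% at every pair of sizes and every ratio tried.

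**Power.** At 38 v 682, r = 0.67 and a difference of 0.35 of the larger group's SD, Student's test has 59% power and Welch's 84%. With equal SDs, where Student's test is right, the price of Welch's is small: 90.5% against 89.0% at 38 v 682 (difference 0.54 SD), and 89.9% against 89.2% at 38 v 160 (difference 0.585 SD).

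**The case against.** Much of the other side stands.

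- Unequal spread is assumed. Without SDs, neither the size nor the direction of the error is known. The two hints point in opposite directions: a mixed control group suggests more spread in the large group (a conservative test), well people at one end of a scale suggest less (a liberal test).
- Bounded, skewed scores such as the HIT and ABNAS would probably go to the rank test under 7.3, so the Student figures apply to whatever outcomes are treated as normal.
- The sizes in 7.2 are expected enrolments, not returned questionnaires. Section 6.4.5 adds healthy controls and reports an early comparison with 20 per group, so the imbalance actually analysed is unknown.
- The raw test is not the only outcome analysis, and a statistical analysis plan may specify more. Even so, the protocol is not silent here: it names the pooled test.

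A reader might infer more than the documents support:

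- *That the level fails whenever spreads differ.* It takes unequal size and unequal SD together. At 25 v 25 nothing happens, and at 160 v 223 the departure is modest.
- *That Mann-Whitney is invalid and must be replaced, for instance by Brunner-Munzel.* Mann-Whitney is valid for the null of identical distributions and misses 5% here only if read as a test of equal medians. Section 7.3 does not say it will be read so and offers it only as an example. Brunner-Munzel would be a preference.
- *That 18 v 682 is the relevant contrast.* The 18 VZV cases fall below the protocol's own minimum of 25.

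**Conclusion.** The point holds in a limited form. Section 7.3 names a pooled-variance test for groups expected to be very unequal, so its level depends on equal SDs, which the protocol nowhere states or supports. At an assumed SD ratio of 1.5 the type I error is about 12-13% at 38 v 160 and 17% at 38 v 682. At 0.67 it is about 1.3% and 0.5%, with lost power. These figures assume normal data, a two-sided 5% level, HSV-2 alone as the herpes group, and analysed numbers equal to those in 7.2.

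It would go too far to conclude that the study's reported differences are false or that the phase III endpoint will be chosen wrongly. The primary outcome (7.1.1) is a prevalence and is untouched. Section 6.3.3 calls the longer-term HIT, SF-36 and ABNAS analyses exploratory, and 6.4.5 ties the endpoint choice to serial evaluations, not to a single two-group p-value. This is a minor improvement.

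**What to change.** In 7.3, replace Student's t test with Welch's unequal-variance t test, or with heteroscedasticity-robust standard errors where a linear model is used, and report each difference with the confidence interval from the same method. Keep Mann-Whitney, adding that it is read as a test of whether the distributions differ and not as a test of equal medians.

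The cost is one or two sentences. It needs no new data and no change to the sample size, and loses about one percentage point of power if the SDs are in fact equal.

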5 ENROLMENT

5.1 Screening

Screening criteria

- a) Over 16 years of age
- b) Suspected meningitis

Patients will be screened from participating hospitals when they have suspected meningitis (see definitions).

They will be allocated a screening number (including the site number) e.g. 01001 for site number 01, screening number 001.

They can be considered for inclusion in the study either by the admitting clinical teams (on clinical suspicion of meningitis), or by the diagnostic microbiology services (when they receive a CSF sample for analysis).

E.g.

Screening point 1:

A clinician identifies a patient that meets the inclusion criteria.

Screening point 2:

A laboratory identifies a CSF sample that is received in the microbiology department. The patient can then be screened for eligibility with regard to the inclusion criteria and clinically suspected meningitis.

Enrolment should occur within the same admission as the above tests are done.

A screening register or log will be required at each site and reasons for non-inclusion will be listed in the screening log. Screening log will be kept at site and at coordinating centre.

Definitions

SUSPECTED MENINGITIS

Illness for 3 weeks or less with:

Headache and one or both of:

- neck stiffness
- photophobia

*except for those with very sudden onset severe headache (defined as no pain to maximal pain within one minute).

OR

Other patients with symptoms in whom the clinician feels a lumbar puncture is needed to diagnose/exclude meningitis

MENINGISM

Headache with neck stiffness and/or photophobia

CSF ≤ 4 leukocytes per ml of CSF**.

(NB some of these patients may have positive microbiology/virology)

ASEPTIC MENINGITIS

Suspected Meningitis (as above), AND

Negative Cerebrospinal fluid (CSF) microscopy and culture for bacteria (or negative PCR for bacteria if on antibiotics prior to CSF sampling), AND

CSF white cell count of 5-1000 leukocytes per ml of CSF** (with a lymphocyte predominance unless total leucocyte count < 20)

and a CSF / Plasma glucose ratio of $> 40\%$ (if paired glucose taken).

WITH NO IMPAIRMENT OF CONSCIOUSNESS

(NB this group may be further subdivided into infective and non infective causes. If there are significant numbers of migraine in this group then they may also be separated out for purposes of analyses.)

PROVEN VIRAL MENINGITIS

Suspected meningitis, AND

CSF white cell count of >4 leukocytes per ml of CSF**

Positive CSF PCR for viral pathogen (or intrathecal antibody).

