7.1.2 Secondary

- a. Time to fever resolution
- b. Resolution of acute morbidity (using the TMS)
- c. Incidence of relapse and recurrence
- d. Change in Headache Impact Test over the study period
- e. Quality of Life Assessment (SF36)
- f. Neuropsychological Outcome (ABNAS)
- g. Economic Analyses (EQ5D)
- h. To determine the number of people with aseptic meningitis being offered an HIV test and the proportion of these that are positive.
- i. Pathogen Specific Outcomes
- j. Clinical Predictors of outcome or pathogen.

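### Section 7.3 gives Cox regression as an example of logistic regression for pathogen, which has no event time, and names only a log-rank test for time to symptom resolution, where Cox regression would fit

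*Protocol*

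**What the plan says.** Only the protocol was available; any separate SAP was not seen.

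On pathogen, section 7.3 says: "Multiple logistic regression e.g. Cox regression, will be used to look for features predictive of particular pathogens". The next sentence adds: "This will be adjusted for age and gender". The matching entry in section 7.1.2, item j, is wider: "Clinical Predictors of outcome or pathogen".

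Section 5.1 defines pathogen status by laboratory findings. Proven viral meningitis needs, besides suspected meningitis and a raised CSF white cell count, "Positive CSF PCR for viral pathogen (or intrathecal antibody". Proven bacterial meningitis needs "Detection of appropriate bacterial pathogen from blood or CSF (culture, nucleic acid detection or serology". Neither definition has a time origin or an event time.

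On the outcomes that are times, section 7.3 says: "Differences in median time to symptom resolution between groups will be analysed using two-sided actuarial (log-rank) methods", at the 5% level. It then says that the outcome analysis is to be adjusted for research site by multi-level modelling, without naming the model. Section 6.3.1.3 collects the Charlson index so that outcomes can be compared in the light of comorbidity. Time to fever resolution is a separate secondary outcome (7.1.2, item a; defined in 6.3.1.1). Section 7.3 does not mention it.

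**The concern.** Logistic regression models the probability of a category. Cox regression models the hazard of an event over follow-up and needs a start time, event times and a rule for censoring. One is not an example of the other. A patient's pathogen is a fixed state at presentation, merely detected by a test, so a hazard ratio for having HSV-2 has no meaning.

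The same section then leaves time to symptom resolution, which does have event times and censoring, with a log-rank test and no named regression model. The groups compared (viral, bacterial, non-meningitic controls) are not randomised, so age, comorbidity and site can differ between them. The protocol itself says it wants to account for site and comorbidity, yet the one model it names that could do so for a time outcome is attached to pathogen.

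At stake are the pathogen-predictor analysis and the comparison of recovery times. Both feed the stated objective of designing a phase III study in herpes meningitis.

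**Working it through.** **1. Outcomes set against the methods named for them**

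| Outcome | Kind of data | Method named in 7.3 | Fit |
|---|---|---|---|
| Pathogen (7.1.2 j; defined in 5.1) | Category | Multiple logistic regression, with Cox as its example; age and gender | Logistic fits; Cox does not |
| Time to symptom resolution (7.1.2 b; 6.3.1.2) | Time; unresolved patients are censored when the daily score ends | Log-rank; site adjustment promised, model not named | Log-rank fits an unadjusted comparison only |
| Time to fever resolution (7.1.2 a; 6.3.1.1) | Time in days | None specifically | Open |
| Predictors of outcome, as distinct from pathogen (7.1.2 j) | Depends on the outcome | None | Open |

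A log-rank test takes a group, a time and a censoring indicator. It can be stratified, so site could in principle enter as strata, but that is not the multi-level model 7.3 promises. It takes no covariates, so age, gender and the Charlson index cannot be entered.

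**2. What happens if Cox regression is run on pathogen**

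Inputs: expected HSV-2 cases 38 among 223 with aseptic meningitis (section 7.2). Assumptions, not from the protocol: a binary feature present in 50% of patients, true odds ratio 3.

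- Overall share: 38/223 = 0.170.
- Let p0 and p1 be the risks without and with the feature. Solve (p0 + p1)/2 = 0.170 and p1/(1 − p1) = 3 × p0/(1 − p0). This gives p0 = 0.097 and p1 = 0.244.
- Odds ratio: (0.244/0.756)/(0.097/0.903) = 3.0. This is the target of logistic regression; a fit to 200,000 simulated patients returned 3.03.
- Cox regression needs a time. If every patient gets the same dummy time, then with Breslow's handling of ties the partial likelihood is maximised at exp(β) = (d1/n1)/(d0/n0), where d and n are cases and patients with (1) and without (0) the feature. That is the risk ratio: 0.244/0.097 = 2.5. A fit to 20,000 of the simulated patients returned 2.53, equal to the risk ratio in that sample.
- If a real time such as length of stay were used instead, the coefficient would mix pathogen with that time.

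So the same sentence can yield about 3.0 or about 2.5 from the same data, depending on which of its two named models is run. The size of the gap depends on the assumed odds ratio and feature frequency.

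**3. Whether any sample-size figure depends on this**

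Section 7.2 says that "a minimum of 25 patients would be needed in each group to have 90% power to show a" difference of one standard deviation, with about 10% drop-out. Normal approximation, two-sided 5%: n = 2 × (1.960 + 1.282)² = 21.0, taken up to 22; 22/0.9 = 24.4, taken up to 25. The stated 25 per group reproduces. It is a comparison of means and does not use either regression model.

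**The case against.** The strongest reply is that this is a drafting slip. The main term in the sentence is multiple logistic regression, which suits a binary pathogen outcome, and a competent analyst would use it. Because item j of 7.1.2 covers outcome as well as pathogen, two intentions may have been run together: Cox for outcome, logistic for pathogen. That is plausible, but the text does not say it and no other section corrects it. The wrong example still stands.

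A reader might infer that the plan cannot answer the pathogen question at all, or that item j is bound to produce meaningless hazard ratios. The protocol does not support that: the logistic model it names is suitable. Only the Cox example fails.

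A reader might also infer that recovery times are to be compared with no adjustment and are therefore left confounded. That goes too far as well. Section 7.3 promises site adjustment and 6.3.1.3 intends a comparison with regard to comorbidity. The narrower point is that the test named for the time outcome cannot deliver either.

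Nor do the expected counts in 7.2 show that pathogen models would be overfitted. They are for one year in 31 centres and are described as a likely underestimate, whereas the protocol summary now gives 35–45 sites and an extension to 5 years. The protocol also fixes no number of candidate features.

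Two further replies have weight. Reporting medians beside a log-rank p-value is ordinary practice, and loose wording there changes nothing. Model form and covariate lists are often left to an SAP, so the silence on fever resolution would not be a point by itself. It is noted because the same rewrite settles it.

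**Conclusion.** The point holds in limited form. Section 7.3 states something wrong: Cox regression is not an example of logistic regression and does not apply to pathogen as section 5.1 defines it. The logistic regression in the same sentence does apply. For time to symptom resolution, the log-rank test named cannot carry the multi-level site adjustment or the intended comorbidity comparison, and no method is named specifically for time to fever resolution.

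The mislabel and the limits of the log-rank test follow from the wording and the nature of the methods, and rest on no numerical assumption. The illustrative gap (odds ratio 3.0 against 2.5) rests on the protocol's 38/223 and on the assumed feature frequency and odds ratio.

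The point affects secondary outcomes only. The primary outcome, prevalence of viral meningitis and the contribution of each virus, is untouched, and so are all sample size and power figures. It should be fixed but is not critical.

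**What to change.** Rewrite two sentences in section 7.3.

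- Pathogen: delete the Cox example. State logistic regression, or multinomial logistic regression if several pathogens are modelled together, adjusted for age and gender.
- Time to symptom resolution and time to fever resolution: state Cox regression adjusted for age, gender and the Charlson index, with site as a frailty term or as strata. Keep the log-rank test as the unadjusted comparison.

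The cost is the redrafting. Age, gender, site and the Charlson index are already available, so no new data are needed and no sample size changes.
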